Compare the serologic responses to cell culture-based quadrivalent influenza vaccine (ccIIV [Flucelvax]) versus live attenuated quadrivalent influenza vaccine (LAIV [FluMist]) in a randomized controlled trial (RCT) among racially diverse children/young adults 4-21 years of age. The primary endpoint is change in antibody titer. The secondary Aims are to: 1. Compare the immune responses between ccIIV and LAIV; 2. The nasal microbiome may both effect and be affected by vaccination (2019 only);

Methods: An unblinded, randomized controlled trial will be conducted by Pediatric and Family Medicine teams at the UPMC and the University of Pittsburgh. Randomization to either LAIV or ccIIV on a 1:1 ratio will be done in blocks of 4. Depending on funding, up to 240-260 will be randomized; assuming a 16% drop-out rate (21% in children under 9 and 11% in ages 9 and up) this would result in approximately 200 participants. Efforts will be made to recruit/include children 4-8 years and persons not vaccinated in 2019-20 for comparison of immune response to those previously vaccinated in 2019-20. Young persons aged 4-21 years without a contraindication to LAIV who plan to receive seasonal influenza vaccination at one of our recruiting sites are eligible to participate. The primary endpoints are change in antibody titers. Given that LAIV is known to produce limited IgG [4], other potential beneficial responses to nasal administration of intranasal LAIV compared to ccIIV will be examined as secondary endpoints, including changes in serum IgA. Titer levels will be log transformed and reported as seropositivity, mean fold rise (MFR) and seroconversion. Specimens will be collected on a subset of participants for cell-mediated immune responses to be studied at CDC and Pitt.

Introduction

Influenza is a major public health burden, each year causing millions of illnesses and outpatient visits and tens of thousands of hospitalizations and deaths in the U.S. The primary influenza prevention method is vaccination; however, influenza vaccine effectiveness (VE) is variable. Host factors (e.g., age and antibody landscape), environment (e.g., tobacco exposure), virus and vaccine characteristics, such as the match between the vaccine and circulating strains and the type of vaccine, contribute to VE. The Advisory Committee on Immunization Practice (ACIP) sets civilian immunization policy for the United States and has no preference among influenza vaccine products [5]. This project will quantify pre- and post influenza immune response to different influenza vaccine types.

LAIV has a storied past. When the formulation was still a trivalent one, a meta-analysis showed LAIV to have superior VE and, for one season, was the ACIP preferred vaccine for children 2-8 years of age [6]. LAIV was previously shown to be more effective than IIV against antigenically different or drifted strains—thus, egg-based LAIV may provide broader protection than IIV. However, after introduction of the quadrivalent formulation, data from 2015-16 showed that LAIV's effectiveness was low in those aged 2-17 years [7], resulting in ACIP recommending against its use [8]. The manufacturer has since reformulated LAIV, specifically the H1N1 component, and it was included as a vaccination option in ACIP's recommendations, starting in 2018-19 [5]. However, its late reintroduction and initial disagreement by AAP and AAFP with the return to routine use, led to limited uptake in the US.

In a community trial of trivalent products in adults aged 18-49 years in 2007-8, IIV was efficacious whereas LAIV was not [9]. In a military population in 2006-7, the duration in years of being vaccine-naïve was correlated with trivalent LAIV effectiveness but not with trivalent IIV effectiveness [10] and the effect of vaccination was statistically significant for LAIV ($P=0.04$) but not for TIV ($P=0.63$).

Cell-culture inactivated influenza vaccine (Flucelvax) was approved by the FDA in 2012, and includes cell seed strains for all four components starting in 2019-2020. CcIIV most closely approximates the antigenicity of the influenza viruses circulating at the time of vaccine strain selection [11]. Among elderly persons in 2017-18, vaccine effectiveness was 10% greater for cell-cultured influenza vaccines relative to egg-based quadrivalent vaccines [12], however limited data are available for children and teens.

There are several factors that may complicate the serological immune response to LAIV. Compared to adults, children have been shown to have a significant IgA response to LAIV [4] which may afford protection not demonstrable by IgG levels alone. In addition, the presence of different microbial species in the nose, as well LAIV-related

alterations in the microbial species present in the nose, may result in variations in IgA antibody production [13].

Another consideration in vaccine response is the individual's prior vaccine history. Both T cells and B cells are required for effective immunity to influenza infection and vaccination. B cells secrete antibodies, which represent a major likely correlate of vaccine-mediated protection. T cells play two potential roles: first, CD8+ T cells can directly recognize and kill influenza-infected cells, and second, antibody production requires "help" from CD4+ T cells. The relative contributions of CD8+ and CD4+ T cells to influenza immunity in humans is less clearly understood than is the role of B-cell-secreted antibodies, but all these responses are likely to be important in controlling influenza virus replication. Children are likely to have different immune response profiles against influenza from adults, since each person's immune "repertoire" is shaped by his/her lifetime exposure to influenza viruses. Most adults have been infected with and/or vaccinated against influenza multiple times in their lives. Therefore, they enter each influenza season with a pre-existing repertoire of "memory" responses against virus strains to which they have been exposed previously, which may cross-react to varying degrees with antigens in the current season's vaccine. In contrast, children have few or no lifetime influenza infections and have fewer pre-existing memory responses when infected or vaccinated. A better understanding of the humoral and cell-mediated immune response to repeat influenza vaccination and different influenza vaccine types (LAIV and cclIV) in children and teens with and without a recent history of vaccination is needed.

This study is the first head-to-head comparison of the current versions of LAIV and cclIV, both of which are FDA-approved options for children aged 4 years and older. We will compare the differences in response among children/teens who were unvaccinated in the previous year in a randomized trial. We will also focus our recruitment efforts on children ages 4-8 years old, regardless of prior vaccination status, as this group was under-represented in 2019-20. The data on responses to repeated doses of cclIV and of LAIV are limited and this study will enable determination of those responses by reenrolling persons who were enrolled in this study in 2019-20 and randomly assigning them to receive LAIV or cclIV.

A. Specific Aims:

Primary Aim

Compare the serologic responses to cell culture-based quadrivalent influenza vaccine (ccIV [Flucelvax]) versus live attenuated quadrivalent influenza vaccine (LAIV [FluMist]) in a randomized controlled trial (RCT) among racially diverse children/young adults 4-21 years of age. The primary endpoint is change in antibody titer.

a. Serology—based on hemagglutination inhibition assay (HAI) titers: Hypotheses: Mean fold rise (MFR) based on HAI titers and seroconversion will differ between LAIV and ccIV.

Secondary Aims:

1. Compare the immune responses between ccIV and LAIV.
2. The nasal microbiome may both effect and be affected by vaccination (2019 only)

B. Study Design and Methods

B.1 Study Design and population Years 1 and 2 combined

1. Total number of subjects to be enrolled at this site up to 480 enrolled over two years (of up to 650 screened)
2. Describe and explain the study design:
This study will be an unblinded randomized controlled trial of 200-220 (2019) and up to 260 (2020) children, adolescents and young adults to examine their immune response following influenza vaccination. For 2020, all participants will have a baseline draw and a Day 28 (range 21-35 days) blood draw. A subset of up to 120 participants ages 9-21 **only** will have a blood draw on Day 7 (range 6-9 days)
3. Describe the primary and secondary study endpoints:
Primary:
-Seroconversion based on hemagglutinin inhibition (HAI) titers
Secondary:
- Day 0 and Day 28 Seroprotection based on HAI titers
- Day 0 and Day 28 geometric mean comparisons of HAI titers

The overall purpose is to understand immune responses related to influenza vaccination and their determinants. We will also look at serum IgG and IgA, cell mediated immunity indices, transcriptomics, genomic, protonomic, cell-mediated immunity, nasal microbiome (2019 only) and/or past vaccine experience effects on the immune response to influenza vaccination.

B.2 Study Design and Population Year 2 2020-2021 only

This study will be a randomized controlled trial of up to 260 children, adolescents and young adults to examine their immune response following influenza vaccination. All participants will have a blood draw at baseline and at Day 28 (range 21-35 days). A subset (up to 120) of participants ages 9 -21 will have a blood draw at Day 7 (range 6-9 days).

Actual recruitment numbers depend on when study can start and pandemic restrictions in place at the time of the study because a) the Day 28 blood draw should be completed before the influenza disease season so that influenza infections do not impact laboratory results; and b) the main student body is leaving the University in mid November per 2020 University policy. Therefore, we anticipate a possible enrollment decrease of 10% per week, given that the enrollment period has been shortened); and c) extra protections in place for participant and worker safety; this limits throughput due to the extra cleaning and social distancing requirements. (The University has granted official permission for this study in the Fall of 2020 after special application).

Recruitment and enrollment of the study population will take place at family medicine and pediatric clinics as well as at other sites, such as the University of Pittsburgh.

Screening for eligibility will be conducted by a Research Assistant either via phone, online, or in person with data entered directly into REDCap, a secure online database management system. (For screening eligibility surveys that are conducted via paper, information collected on this form will be entered into REDCap post-hoc.) Research assistants will meet with parents of potentially eligible children, or young adults themselves, to review study requirements and the consent form, giving parents/patients time to read through it thoroughly and answer questions. Then research assistant will obtain parental or young adult consent and child/teen assent. For research assistants without medical training, a physician or doctoral level pharmacist will be available either in person or via electronic device to review the study protocol and vaccine choices and answer any questions the parents and/or child/teen or young adult may have.

Remotely, written informed consent may also be collected after performing screening procedures, but prior to performing any of the research interventions/interactions. A REDCap PDF of the consent form will be emailed to the potential participant and reviewed with them. The participant receives the email and clicks on a link to see the consent. If they agree, they initiate the electronic consent process within REDCap, sign and submit the form. The signed consent document is stored securely in REDCap. The consenting party will document that they consented the participant by going back into the participant's consent to complete the fields on the electronic consent form or by a note to file in the participant record.

B.2.1 Inclusion and Exclusion Criteria

A. Inclusion criteria:

For 2019 Enrollment

1. Persons aged 4-21 years who have not received 2019-2020 vaccination and meet one of the following criteria:
 - a. Denied vaccination in 2018-19.
 - b. Participated in our 2018-19 study of childhood influenza vaccine.

- c. Contingency if enrollment low: Persons with record-confirmed type of influenza vaccination in 2018-19.
2. Willing to receive seasonal influenza vaccine by randomization to LAIV or cclIV;

For 2020 Enrollment

1. Persons aged 4-21 years who have not received 2020-21 season influenza vaccination;
2. Willing to receive seasonal influenza vaccine by randomization to LAIV or cclIV;

B. Exclusion criteria:

1. Unable or unwilling to complete all required study activities, including informed consent and bloodwork;
2. Have a known immunocompromising condition or taking high doses of an immunosuppressant medication (e.g., high dose steroids defined as ≥ 20 mg prednisone equivalent per day for >2 weeks);
3. Known to be pregnant;
4. Have a history of severe allergy to eggs or to influenza vaccine or any of its components.
5. Chronic use of aspirin or aspirin containing medication
6. In the last twelve months, have had asthma, wheezing, treatment for heart disease, treatment for seizures, or treatment for diabetes mellitus.
7. Participants who would place at risk (due to FluMist as a live attenuated vaccine) severely immunocompromised persons as a household or close contact.

B.2.2 Enrollment

Targeted enrollment numbers

Targeted enrollment is up to 130 individuals in each vaccine arm for 2020.

Approximately $\frac{1}{2}$ of the subjects would be recruited from our returning 2019-2020 vaccinated cohort of patients with three prior visits. Among non-cohort recruits, we will prioritize persons ages 4-8 years regardless of 2019-20 vaccination status and persons 9-21 years who were not vaccinated with seasonal influenza vaccine in the 2019-20 season. Enrollment in this study will begin after IRB and CDC approval is obtained and will continue until the target sample size for each group is reached with the goal of completing all baseline study visits by mid November of the current year. We will recruit from primary care and pediatric locations such as UPMC Shadyside Family Health Center; Children's Community Pediatrics (CCP) Primary Care Oakland; and, perhaps, East Liberty Family Health Center. We will also recruit past participants who were vaccinated at Falk Pharmacy. Because the Pitt+Me database was highly successful in 2019-20, we will use it to recruit new participants. Inclusion of older teenagers and young adults aged 18-21 years allows for college students using Falk pharmacy, as well as returning cohort members.

B.2.4 Enrollment procedures: Data and Blood Sample Collection

B.2.4.1a Enrollment visit

Eligible patients who agree to enroll will be consented prior to conducting further baseline visit enrollment procedures. Written informed consent includes permission to access medical records and/or state registry records to obtain data related to medical history, medication use, vitals, high-risk codes, and vaccination history.

A survey of demographics and health status will be collected at baseline, or if insufficient time, at a follow-up study visit. Data will be entered directly into REDCap (or if collected via paper will be entered into REDCap post-hoc.)

All participants will have blood drawn at baseline enrollment visit (may be done during the summer prior to vaccination). Refer to Table for blood volumes and tube types to be collected. The total blood volume for a particular participant is based on several factors including size of the participant's veins, limitations on number of PBMC specimens that the lab can process in a particular day, past PBMC yield from the participant (if known), enrollment site, past vaccination status, and courier transportation availability, given the need to process PBMCs quickly.

Upon consent, participants will be randomized to one of two vaccine types (LAIV or cclIV) using a 1:1 computer generated simple randomization scheme. Randomization block size will be conducted in sets of four (2 LAIV and 2 cclIV).

Table. Specimens to be collected for 2020

Age Group	Blood tube type	Day 0 visit	Day 7 post vax visit	Day 28 post vax visit	Total
4-8 years	SST Serology	5-10 mL	No visit	5-10 mL	10-20 mL
	CPT-PBMCs	4 mL	No visit	4 mL	8 mL
9-21 years	SST Serology	10 mL	--	10 mL	20 mL
	CPT-PBMCs on subset	24 mL	24 mL	24 mL	72 mL

B.2.4.1b Vaccination visit

All participants will receive influenza vaccine after the pre-vaccination blood draw according to their randomized influenza vaccine allocation. Both vaccines are FDA approved, licensed and recommended for these age groups. Vaccinations will be recorded in the EMR and Vaccine Information Sheets will be provided following standard clinical protocol. This visit may occur at the time of the enrollment visit provided that the vaccine to which the participant is randomized is available.

B.2--4.1c Blood draw procedures

All blood will be collected by trained personnel with experience drawing blood from children. The blood samples will be collected using Vacutainer tubes, appropriate for type of processing, and appropriately labeled with a uniform scheme (including study ID and collection time point).

Serum specimens will be aliquoted and frozen. Individual aliquots will be either shipped to CDC for analysis, analyzed by labs affiliated with the University of Pittsburgh or UPMC, or banked for future studies that might involve proteomics, immunology, transcriptomics, or genomics. .

B.2.4.2 Follow-up study visits

All participants will have a blood draw at Day 28 (range 21-35 days). A subset (up to 120) of participants ages 9 -21 will have a blood draw at Day 7 (range 6-9 days).

The amount of blood to be drawn at each timepoint is noted in the Table.

B.2.4.3 Specimen Processing and Sharing with Collaborators

[name] lab at the Rangos Research Building will process all blood specimens for storage and handling following standard protocols by trained study staff. Specimens will be shipped to CDC and CDC's chosen laboratory contractors as well as to other contracted laboratories for processing and analysis.

Flow cytometry results from CDC will be shared with Pitt so that further bioinformatics analyses can be conducted.

B. 3 Laboratory Methods

The laboratory tests consisting of assessing CMI responses including multiparametric flowcytometry of T and B cells, ILC, DC, antigen-specific T cells by ICCS, B-cell seq and Ig-seq to determine antibody clonotypes and their specificities, serological analyses including ADCC, HI, microneutralization, avidity and reactivities against historical strains will be conducted by CDC or CDC's chosen contractors.

B. 3.1 Hemagglutination Inhibition Antibody and Microneutralization Testing

Serum specimens will be tested by hemagglutination inhibition assays (HAI) to estimate antibody titer response against the vaccine strains. HAI testing will be conducted at CDC or by a CDC-designated laboratory. Microneutralization titers may be conducted by CDC for selected antigen(s). Serum antibody levels may be measured by enzyme immunoassays at CDC.

B. 3.2 Peripheral Blood Mononuclear Cells (PBMCs)

PBMC will be analyzed at the CDC laboratory for cell mediated immunity. Briefly, innate immune subsets (NK cells, innate lymphoid cells, gamma/delta T cells), antigen-specific B cell plasmablasts, HA-specific memory B cells, phenotypic (subsets) and functional (cytokine production) characterization of CD4 and CD8 T cells will be done using multiparametric flow cytometry. For the proposed flowcytometric analysis 20×10^6 PBMC with greater than 85-90% viability are required. In addition, analysis of the changes in the B cell repertoire along with Ig-seq with LC/MS in response to prior vaccination status and/or vaccine types will be considered for a subset of vaccinees. For LC/MS, 1.5 ml-2 ml of sera is needed.

B. 3.3 Additional laboratory testing to be done if funding permits.

Pitt may utilize spectral flow cytometry to generate single cell protein expression data. We have recently adapted our flow cytometry panels to take advantage of the Cytex Aurora platform capabilities here at the University of Pittsburgh. This approach utilizes deconvolution of fluorescence data to allow for resolution of overlapping emission spectra. Our current panel for human PBMC is the following 26 antigens: CCR7, CD19, CD16, TCR $\gamma\delta$, CD14, CD8, PD1, CD56, CD4, CD28, CD11c, CD45Ra, CD3, CD25,

IgD, CD95, CD11b, CD38, CD57, CD27, CD123, CD127, HLADR, KLRG1, CD45R0, CD154. With this panel we can identify granulocyte, monocyte, and lymphocyte subsets with high resolution. For example, this panel allows for identification of CD8+ T cells, NKT cells, CD4+ T cells, B cells, NK cells, and lineage negative ILC, further segregated by activation and memory markers. All of this information is derived from a single flow cytometry run on 5×10^6 cells.

Data are analyzed by multidimensional algorithms such as t-stochastic neighborhood embedding (tSNE) or sequential pattern discovery using equivalence classes (SPADE) to cluster cell types based on the full panel of antigens stained rather than typical two dimensional staining analyses. tSNE works by first creating a probability distribution that dictates the relationships between various neighboring data points in high-dimensional space. It then tries to recreate a low dimensional space (two dimensional plot) that follows that probability distribution as best as possible to segregate cells based on similarity of marker expression. SPADE uses a similar approach to determine relationships between individual cells, but relays this information as a two dimensional branching tree plot that indicates the degree of similarity between cells. These algorithms allow for identification in three dimensions of overlapping cell subsets in two dimensional space and consideration of multiple stains at the same time, with the potential to identify new cell subsets.

C. Statistical Analysis

Pre- and post- vaccination geometric mean antibody titers (GMT) will be \log_2 transformed and compared among participants who received LAIV or cclIV. The mean fold rise, seroconversion and seropositivity at Day 28 will be calculated.

Seroconversion will be defined as either a pre-vaccination HAI titer $<1:10$ and a post-vaccination HAI titer $\geq 1:40$ or a pre-vaccination HAI titer $\geq 1:10$ and a minimum four-fold rise in post-vaccination HAI antibody titer.

Fold-rise in HAI titers is the ratio of Day 28 log titers to Day 0 log titers and will be conducted with baseline titer as a covariate.

C.1 Power Analyses

Using a power calculation for a Chi square test with alpha set at 0.05 reveals the following:

Effect size	Final sample size	Power	Comments
0.3	90	.81	Fairly large effect size; unlikely to occur
0.3	81	.77	Fairly large effect size; assumes 10% failure to complete
0.1	81	.15	No power for small effect size
0.2	200	.81	Good power for moderate effect size
0.1	200	.29	No power for small effect size

<https://www.anzmtg.org/stats/PowerCalculator/PowerChiSquare>

If funding is available for the full sample, analyses based on prior 2019-20 vaccine history (none, egg-based, cell-based) will provide additional insight into vaccine immunogenicity.

D. Human Subjects

D.1. Consent

Participants in this study will provide written consent (parents and young adults) and assent (children/teens) as applicable for specimen collection, influenza vaccination, and medical record review.

Further details regarding data privacy and protection of human subjects are provided in the IRB application document.

D.2. Participant Compensation

Participants will be compensated for each visit:

- First visit = \$35 plus \$5 travel for a total of \$40
- Second visit on subset = \$25 plus \$5 travel for a total of \$30
- Final visit = \$45 plus \$5 travel for a total of \$50

The maximum possible payment will be \$90 (two visits)-\$120 (three visits). If a separate vaccine visit is required, participants will be paid \$30 for the blood draw and enrollment visit and \$10 for a separate vaccine visit.

D.3. Threats to study and contingencies

In the event of a late start, some aspects of recruitment may be impacted: (1) PBMCs are time-consuming to process, leading to a limited throughput; thus, the sample size for PBMCs is constrained by starting later. (2) vaccination in the community is likely to start early, due to vaccination by community pharmacies and to mass purchase by UPMC; later recruitment is more difficult because some will have already been vaccinated.

Contingency plans: In the event of a late start, several contingencies will be used. First, a greater emphasis will be given to recruiting young adults, who are less likely to have been vaccinated early. Second, if one vaccine is delayed, then persons may be recruited per the randomization scheme and those randomized to the missing vaccine may have their baseline blood drawn but be asked to return for the rest of the study once the vaccine is available. Third, given that quality processing of the PBMCs is time consuming with limited throughput, overall target sample sizes may be reduced.

D.4 Timeline

	Aug	Sept- Nov	Dec	Jan	Feb-May	June-July
Prep, Supplies, Train						
Enroll, vaccinate, draw blood, process specimens						
Organize and ship to CDC (or Battelle) lab						
Conduct initial HAI						
Advanced Lab assays						

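### Section C's fold-rise formula does not give a fold rise, and the summary, Primary Aim and B.1 do not name the same primary endpoint

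*Combined protocol and SAP*

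**What the plan says.** **Primary endpoint.** The opening summary and the Primary Aim (Section A) both state: "The primary endpoint is change in antibody titer". The summary's Methods paragraph turns to the plural, "The primary endpoints are change in antibody titers", and adds: "Titer levels will be log transformed and reported as seropositivity, mean fold rise (MFR) and seroconversion". The hypothesis under the Primary Aim is "Mean fold rise (MFR) based on HAI titers and seroconversion will differ between LAIV and ccIV", with no order between the two measures.

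B.1 item 3 is the only place that sorts endpoints into primary and secondary. Its one primary entry is "Seroconversion based on hemagglutinin inhibition (HAI) titers". The secondary entries are seroprotection and "Day 0 and Day 28 geometric mean comparisons of HAI titers". MFR is in neither list. Section C says "The mean fold rise, seroconversion and seropositivity at Day 28 will be calculated" and ranks none of them.

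**Fold rise.** Section C defines it as the Day 28 log titer over the Day 0 log titer, with baseline titer as covariate. The seroconversion definition in the same section uses a four-fold rise on the titer scale.

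**Power.** C.1 tabulates power for a chi-square test at alpha 0.05. It names no endpoint, strain or response rates.

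**The concern.** A fold rise is a ratio of titers, and its logarithm is a difference of log titers. Dividing one log titer by another gives a quantity that depends on the baseline. Two participants with the same four-fold rise get different values, and a reported MFR would not mean what readers take it to mean. About half of the 2020 participants were to come from the cohort vaccinated in 2019-20 and the rest from new recruits, so baselines may well vary.

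On ranking, a report could present either MFR or seroconversion as primary and cite the protocol for it. The trial is unblinded, so a fixed primary endpoint is one of its main protections against selective reporting.

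**Working it through.** **1. The plan's own power figures.** Reading effect size as Cohen's w, with 1 df and noncentrality N × w²:

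| w | N | N × w² | Stated | Recomputed |
|---|---|---|---|---|
| 0.3 | 90 | 8.10 | .81 | 0.812 |
| 0.3 | 81 | 7.29 | .77 | 0.770 |
| 0.1 | 81 | 0.81 | .15 | 0.147 |
| 0.2 | 200 | 8.00 | .81 | 0.807 |
| 0.1 | 200 | 2.00 | .29 | 0.293 |

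All five rows reproduce. With 2 df the fourth row would be 0.718, so the table describes a two-by-two comparison, which fits a binary endpoint such as seroconversion. For two equal arms w = |p1 − p2| / (2√(p̄(1 − p̄))), so w = 0.2 corresponds to 40% v 60% or 20% v 38%. The N of 200 agrees with the summary ("this would result in approximately 200 participants"): 240 × 0.84 = 201.6.

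**2. The fold-rise formula (exact).** For baseline b and true fold rise F, the written formula gives log(bF)/log(b) = 1 + log2(F)/log2(b), in any log base. For F = 4:

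- b = 10: 1 + 2/3.322 = 1.60
- b = 40: 1 + 2/5.322 = 1.38
- b = 320: 1 + 2/8.322 = 1.24

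The log2 difference is 2 each time and back-transforms to 4. If titers below 10 are recorded as 5 (a convention the documents do not state), b = 5 gives 1.86. Back-transforming the ratio does not help: 10 to 40 gives 2^1.602 = 3.04, and no change gives 2^1 = 2.

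**3. Simulation assumptions.** The documents give no SDs or response rates, so all of these are assumed: one strain; 100 per arm; baseline log2 titer normal with mean log2(20) and SD 2; titers floored to two-fold dilutions; values below 10 set to 5; seroconversion as in Section C. The tests are chi-square on seroconversion and ANCOVA of Day 28 log2 titer on arm and baseline, which gives the same arm effect as the log2 difference with baseline as covariate.

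**4. No true difference, either test at p < 0.05 (10,000 replicates).**

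- Shift models (mean log2 rise/SD 1.0/1.3, 1.5/1.5, 1.2/1.7; slope −0.3 on baseline): 0.082, 0.078, 0.081.
- Responder mixtures (30%, 50%, 30% responders; mean rise 3, 3, 4; SD 1.2, 1.2, 1.5; non-responders mean 0, SD 0.5): 0.077, 0.072, 0.072.

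**5. True difference near w = 0.2 (8,000 replicates), power.**

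| Scenario | Seroconversion | Log2 difference | Formula as written |
|---|---|---|---|
| Shift 1.0/1.3, arm effect 0.73 | 0.793 | 0.953 | 0.918 |
| Shift 1.5/1.3, arm effect 0.73 | 0.827 | 0.954 | 0.916 |
| Shift 1.5/1.5, arm effect 0.83 | 0.835 | 0.957 | 0.923 |
| Shift 1.2/1.7, arm effect 0.95 | 0.839 | 0.961 | 0.932 |
| Mixture 20 v 43% | 0.822 | 0.828 | 0.794 |
| Mixture 30 v 54.5% | 0.809 | 0.820 | 0.777 |
| Mixture 20 v 41% | 0.838 | 0.802 | 0.764 |
| Mixture 40 v 63.5% | 0.796 | 0.781 | 0.733 |

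The mixtures use mean rises of 3, 3, 4 and 3.5 with SDs of 1.2, 1.2, 1.5 and 1.3. Seroconversion has 0.12 to 0.16 less power than the log2 analysis in the shift models, and is within 0.04 of it in the mixtures. The formula as written loses 0.03 to 0.05 against the log2 difference. Reference-arm true MFRs of about 1.5 to 2.5 are reported as 1.16 to 1.41.

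**6. Price of two primaries.** At alpha 0.025, N = 200 and w = 0.2, chi-square power is 0.72 (Bonferroni). Holm lies between that and 0.81. In the scenarios above Holm cost about 0.01 (shift) to 0.04-0.06 (mixture).

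**The case against.** The best defense is that the plan does settle the ranking. B.1 item 3 is the only ranked list and names one endpoint, seroconversion is itself a change in titer, and the only powered test suits a binary outcome. This narrows the conflict, and Section C, which ranks nothing, contradicts nothing. It does not remove the conflict. If change in titer is an umbrella term, it covers several measures with no multiplicity rule, against B.1's single one. MFR stays in the primary hypothesis but in no endpoint list.

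The formula may be only a slip, since the same section uses a proper four-fold rise for seroconversion. That is plausible, but it is the only definition of fold rise in the document, and the planned baseline covariate does not turn a ratio of logs into a fold rise.

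Three stronger readings are not supported:

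- A reader might infer that the formula invalidates the comparison of arms. In simulations with no true difference its type I error was 0.048-0.056, and seroconversion does not use it.
- A reader might infer an error rate of 1 − 0.95² = 0.0975 for two measures, or 1 − 0.95⁴ = 0.185 for four strains. Both figures assume independent tests. The two measures come from the same titers, strain results would be correlated, and the documents do not say that every strain is tested as primary.
- A reader might infer that the power table is wrong. It reproduces; it only lacks a label.

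**Conclusion.** Both parts hold. The formula is wrong as written, by exact arithmetic: it understates every rise at usual HAI baselines, and more so the higher the baseline. This affects reported MFR, not seroconversion.

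The primary endpoint is inconsistent on the face of the text. Its consequence is smaller: a false-positive rate of about 0.07-0.08 instead of 0.05, for one strain and 100 per arm, and only if the primary is picked after results are seen. The documents do not show that this was intended. Confidence is high for the wording and the formula. The simulated sizes depend on the assumed titer distributions.

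**What to change.** Before HAI analysis:

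1. In Section C, define fold rise as Day 28 titer divided by Day 0 titer. Analyze it as the difference in log2 titers with baseline log2 titer as the covariate already planned, and back-transform for reporting.
2. State one primary endpoint in identical words in the summary, Primary Aim, B.1 and Section C, and give MFR an explicit place. Seroconversion is the default, because B.1 names it and the C.1 table fits it. Label that table as seroconversion, with illustrative rates such as 40% v 60%.
3. State which of the four vaccine strains the primary endpoint covers. If more than one strain is primary, or if MFR and seroconversion are both primary, specify a multiplicity rule such as Holm.

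**Cost.** Steps 1 and 2 are wording and labels, with no new data. Choosing seroconversion may give up 0.12-0.16 power against baseline-adjusted log2 titer if responses shift uniformly, and little if they follow a responder mixture. The sponsor may therefore prefer the titer endpoint, but would then have to replace the chi-square power basis in C.1. With two primaries, chi-square power at N = 200, w = 0.2 could fall from 0.81 to as low as 0.72.
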